Statistical methods:	
The choice of statistical analysis method will be determined by the type of raw data, type of distribution. The feasibility of using a number of statistical methods will be assessed after data collection has been completed, as the nature of the data distribution, sample homogeneity, etc. is not known in advance. During the course of the analysis, it is possible to expand the list of methods used, if necessary for qualitative data processing.
 
Statistical processing of data obtained during the trial will be performed using the R statistical programming language (version 3.4.4 or higher) and/or SAS statistical software (version 9.4 or higher), or other specific applicable software that ensures the appropriate quality of the data obtained.
 
The following population groups will be used for the analyses:
 
 1. The ITT (Intent-to-treat) population will include all randomized patients regardless of investigational product/placebo administration. 2. The mITT (modified Intent-to-treat) population will include patients who have completed the full course of therapy regardless of the presence of Protocol violations/abnormalities. 3. The PP (Per protocol) population will include patients who completed the trial in accordance with the Protocol. 
At the stage of statistical data processing, additional analyses of the efficacy and/or safety of investigational product/placebo in subpopulations of patients of different age groups can be performed.
 
Analysing efficacy data:
 
The primary population for the evaluation of efficacy criteria, proof of the hypothesis of superiority of the trial drug therapy over placebo based on the primary efficacy criterion score, will be the PP population.
 
Additionally, efficacy criteria will be analysed in the ITT and mITT populations.
 
This approach in selecting the population for analysis is based on the design of the planned clinical trial: patients in both the investigational product and placebo groups will receive standard (baseline) therapy (according to the Clinical Guidelines "Ischaemic Stroke and Transient Ischaemic Attack in Adults", 2015) with proven efficacy. In this regard, the use of the ITT population for a more conservative assessment of therapy is inappropriate, as this approach markedly levels the clinical effects of investigational product, therefore, to compensate for the therapeutic effects of baseline therapy and to properly assess the effects of investigational product, as the main population for the analysis of efficacy parameters in the planned

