9. STATISTICS

9.1. Calculation of sample size

The sample size calculation was based on the results of the Phase III clinical trial of Mexidol® [Multicentre randomized double-blind placebo-controlled parallel-group trial of the efficacy and safety of MEXIDOL® (solution for intravenous and intravenous administration / coated tablets) in long-term sequential therapy in patients with hemispheric ischaemic stroke in

the acute and early recovery periods - (EPICA)] dated 30.09.2016.

The trial plans to test the hypothesis of "superiority" of therapy with the investigational product vs. placebo therapy. The following indicator was chosen as the primary efficacy criterion: "The magnitude of change in the patient's **mRS** (Modified Rankin Scale) score at the end of therapy (Day 71) vs. baseline (in points)"

In the case of a superiority trial, the null hypothesis (H_0) and the alternative hypothesis (H_1) are formulated as follows:

$$H_0: \varepsilon = \mu_T - \mu_p \leq \delta, H_1: \varepsilon > \delta, \delta > 0, \text{ where}$$

- ε is the true difference between the value of the primary efficacy index (μ_T) in the group of patients taking the investigational product (T) and the value of the primary efficacy index (μ_p) in the group of patients taking placebo,
- δ - the boundary of "superiority" of therapy with the investigational product compared to placebo therapy by the primary efficacy indicator.

To prove superiority of therapy with an investigational product compared with placebo therapy, the lower bound of the 95% one-sided confidence interval (CI) for the difference in values of the primary efficacy criterion ($\mu_T - \mu_p$) must be greater than δ , where $\delta > 0$, i.e. CI must fall within the interval $(\delta, +\infty)$.

To calculate the sample size, data from the EPICA clinical trial were used for the ITT population (patients who received the investigational product or placebo at least once), as this population allows us to draw conclusions about the efficacy of the investigational therapy on the population closest to the patient population in real clinical practice. The results of the previously conducted EPICA clinical trial are summarized in Table 9.1.

Table 9.1. *Change in mRS score at the end of therapy relative to baseline [Visit 1 (Day 1) to Visit 5 (Day 67-71)] in patients enrolled in the ITT population.*

[μ - arithmetic mean; SD - standard deviation, DM - difference in mean averages]

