9.4. Dealing with dropped out, excluded patients and missing data

No missing data will be completed, missing data will not be taken into account when performing statistical analyses.

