9.6. Population to be analysed

The following population groups will be used for the analyses:

1. The ITT (Intent-to-treat) population will include all randomized patients regardless of investigational product/placebo administration.
2. The mITT (modified Intent-to-treat) population will include patients who have completed the full course of therapy, regardless of the presence of Protocol violations/ deviations.
3. The PP (Per protocol) population will include patients who completed the trial in accordance with the Protocol.

At the stage of statistical data processing, additional analyses of the efficacy and/or safety of investigational product/placebo in subpopulations of patients of different age groups can be performed.

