9.7.2. Statistical methods for assessing efficacy

The primary population for the evaluation of efficacy criteria, proof of the hypothesis of superiority of the trial drug therapy over placebo based on the primary efficacy criterion score,

will be the PP population.

Additionally, efficacy criteria will be analysed in the ITT and mITT populations.

This approach in selecting the population for analysis is based on the design of the planned clinical trial: patients in both the investigational product and placebo groups will receive standard (baseline) therapy (according to the Clinical Guidelines "Ischaemic Stroke and Transient Ischaemic Attack in Adults", 2015) with proven efficacy. Therefore, the use of the ITT population for a more conservative assessment of ongoing therapy is inappropriate, as this approach markedly offsets the clinical effects of the investigational product. Therefore, to compensate for the therapeutic effects of baseline therapy and to properly evaluate the effects of IP, the PP population is considered as the primary population for analysing efficacy parameters in the planned trial.

The trial plans to test the hypothesis of "superiority" of therapy with the investigational product vs. placebo therapy. The following indicator was chosen as the primary efficacy criterion: "The magnitude of change in the patient's **mRS** (Modified Rankin Scale) score at the end of therapy (Day 71) relative to baseline (in points)".

In the case of a superiority trial, the null hypothesis (H_0) and the alternative hypothesis (H_1) are formulated as follows:

$$H_0: \varepsilon = \mu_T - \mu_p \leq \delta, \quad H_1: \varepsilon > \delta, \quad \delta > 0, \text{ where}$$

- ε is the true difference between the value of the primary efficacy index (μ_T) in the group of patients taking the investigational product (T) and the value of the primary efficacy index (μ_p) in the group of patients taking placebo,
- δ - the boundary of "superiority" of therapy with the investigational product compared to placebo therapy by the primary efficacy indicator.

To prove superiority of therapy with the investigational product compared to placebo therapy, the lower bound of the 95% (or 97.06% in the case of a phase II trial) one-sided confidence interval (CI) for the difference in values of the primary efficacy criterion ($\mu_T - \mu_p$) must be greater than δ , where $\delta > 0$, i.e. CI must fall within the interval $(\delta, +\infty)$.

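### The mITT set contains only patients who completed therapy, so it cannot show whether the per-protocol result is biased by outcome-related stopping

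*Protocol*

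**What the plan says.** Protocol 9.6 defines three sets.

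- ITT: "population will include all randomized patients regardless of investigational product/placebo administration".
- mITT: "The mITT (modified Intent-to-treat) population will include patients who have completed the full course of therapy, regardless of the presence of Protocol violations".
- PP: "The PP (Per protocol) population will include patients who completed the trial in accordance with the Protocol".

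The synopsis opens its mITT definition in the same way: "The mITT (modified Intent-to-treat) population will include patients who have completed the full course of therapy". The mITT wording has the same content in the Protocol abbreviations and synopsis, and in the SAP abbreviations and section 11, so it is not a slip in one place.

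PP is the primary efficacy population. On the others, Protocol 9.7.2 says: "Additionally, efficacy criteria will be analysed in the ITT and mITT populations". On missing data, Protocol 9.4 says: "No missing data will be completed, missing data will not be taken into account when performing statistical analyses". SAP section 11 also rules out filling in missing data.

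Four other provisions matter.

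- Protocol 5.3 lists recurrent stroke, serious or other adverse events, allergic reaction and any condition the investigator judges to require it as grounds for withdrawal.
- Protocol 6.1 and 6.2 provide an early-withdrawal visit with the same procedures as Visit 4, which include mRS.
- Protocol 5.4.4 leaves patients who never received a dose out of the statistical analysis.
- The mRS form in Appendix 2 scores death as 6.

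**The concern.** Completing 70 days of treatment is a post-randomisation event, and several grounds for withdrawal are plausibly related to recovery on mRS. A patient who dies or is withdrawn during therapy is in neither PP nor mITT. If such patients do worse and the arms differ in how many stop, a comparison of completers is shifted even when the drug does nothing.

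A set labelled modified intention-to-treat is normally read as a check on that problem. Here it repeats the same selection. Agreement between PP and mITT would say only that deviations among completers did not drive the result.

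The remaining check is ITT, and its content is not settled. Depending on how the early-withdrawal mRS is handled, it too could shrink towards patients who reached Visit 4.

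**Working it through.** **1. Who is in each set.** This follows from the definitions.

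| Patient | PP | mITT | ITT |
|---|---|---|---|
| Completed, no important deviation | yes | yes | yes |
| Completed, with deviation | no | yes | yes |
| Dosed, stopped early (including death) | no | no | yes, but use of the exit mRS is not stated |
| Randomised, never dosed | no | no | yes by 9.6; no by 5.4.4 |

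mITT differs from PP only in the second row. The third row is where outcome-related stopping acts, and there PP and mITT are identical.

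**2. The plan's own figures (Protocol 9.1).** The inputs are a difference of 0.292, a margin of 0.027, an SD of 0.802, one-sided alpha 0.05, power 0.80 and 1:1 allocation.

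n per group = 2 × (1.6449 + 0.8416)² × 0.802² / (0.292 − 0.027)² = 7.953 / 0.0702 = 113.3, so 114. The total is 228, and 228 / 0.75 = 304. Both reproduce. The plan therefore allows 304 − 228 = 76 patients (25%) to be missing from PP for all reasons together.

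**3. What the earlier Phase III trial lost (Protocol 2.3.2).** 150 were randomised, 141 completed and 124 were analysed per protocol. Early stopping was 9/150 = 6%. Of the 150 − 124 = 26 lost from PP, 141 − 124 = 17 (65%) were completers, whom an mITT of the present kind would restore. The other 9 it would not.

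**4. Direction and size of a completers bias.** Assume no true difference among all randomised patients, and that stoppers improve by g points less than completers in the same arm. The completers' mean then exceeds the arm mean by p × g, where p is the proportion stopping, so the difference between completers is b = p_T g_T − p_P g_P.

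Take 152 per arm, with 25% stopping on active and 15% on placebo (assumed). Completers number 114 and 129.2, and SE = 0.802 × √(1/114 + 1/129.2) = 0.103. The chance that the one-sided 95% lower bound exceeds 0.027 is 1 − Φ(1.645 − (b − 0.027)/SE).

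| g, same in both arms | b | Chance of false superiority |
|---|---|---|
| 0.5 | 0.05 | 0.08 |
| 1 | 0.10 | 0.18 |
| 2 | 0.20 | 0.51 |
| any, with equal stopping (25% each) | 0 | 0.03 |

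**5. Simulation with stopping linked to recovery.** There are 152 per arm, change is normal with mean 2.0 and SD 0.8 in both arms, and the log-odds of stopping rise by 1.0 to 1.5 per SD of poorer recovery. All stopping rates and the link are assumptions.

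| Stopping, active vs placebo | False gain in completers | False superiority in completers |
|---|---|---|
| 20% vs 10% | about 0.065-0.084 | about 10-15% |
| 8% vs 4% (overall 6%, as in the earlier trial; the split is assumed) | about 0.03-0.04 | about 5-6% |
| equal | about 0 | about 2.4% |
| 10% vs 20% | favours placebo | below 1% |

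If every dosed patient had a valid score, the figure would be about 2.6%. It is below 5% because the bound must clear 0.027 rather than zero.

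**The case against.** The best defence is that the set does what its definition says. It is described as ignoring protocol violations, and it tests exactly that. Nothing in the documents claims that it checks selective stopping. In the earlier trial 17 of the 26 patients lost from PP were completers, so restoring such patients is worthwhile. All of this stands, and it is a reason to keep the set under an accurate name.

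Four stronger readings are tempting, and the documents do not support them.

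- A reader might infer that the plan has no all-randomised efficacy analysis. It has one: ITT, in Protocol 9.7.2 and SAP section 11. The weakness is in its rules, not its absence.
- A reader might infer that no planned set resembles the one behind the sample size, which Protocol 9.1 describes as "ITT population (patients who received the investigational product or placebo at least once". Protocol 5.4.4 removes never-dosed patients, so ITT as operated would be close to a dosed set. The fault is that 5.4.4 and 9.6 contradict each other.
- A reader might treat the 25% allowance as a stopping rate. It covers every loss from PP, deviations included, so stopping rates cannot be judged against it.
- A reader might take a false-superiority figure as a property of this trial. It is not. The result depends on the assumed split between arms, is near the nominal 5% at the earlier trial's overall stopping rate, and reverses if placebo patients stop more often.

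**Conclusion.** The concern holds as a matter of definition. Wherever it is defined, mITT is a completers set. It can test sensitivity to deviations among completers and cannot test whether outcome-related stopping biases PP. That does not depend on any assumed rate.

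The planned ITT analysis only partly fills the gap, because missing values are not filled in, the status of the early-withdrawal mRS is unstated, and 5.4.4 conflicts with the ITT definition.

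The size of any bias cannot be derived from the documents. The 10-15% illustration requires clearly more stopping on active than on placebo and a real link between stopping and poor recovery. With equal and similarly selective stopping there is no bias. The point concerns a supportive population and should be corrected, but it does not show that the primary result would be wrong.

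**What to change.** In the Protocol (abbreviations, synopsis, 9.6) and the SAP (abbreviations, section 11):

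1. Redefine mITT as all randomised patients who received at least one dose, analysed in the randomised arm whether or not therapy was completed.
2. State the score used: the Visit 4 mRS or, for early stoppers, the mRS from the early-withdrawal visit, with deaths scored 6 as on the form in Appendix 2.
3. Do not use the Visit 2 score as the end-of-therapy value in the main mITT analysis. That would carry a Day 11/12 value forward to Day 71. Use it at most in a labelled sensitivity analysis.
4. Keep the present set under the name 'completers', and do not present it as ITT-type support.
5. Reconcile Protocol 5.4.4 with the ITT definition in 9.6.

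The cost is wording, a little more analysis work and possibly a slightly less favourable mITT estimate. No new procedure is needed, because the early-withdrawal visit already includes mRS. Two limits remain. A patient lost without an exit visit still has no score, and an exit score is taken at stopping rather than at Day 71. The redefined set therefore reduces the selection but does not fully reach the 2.6% case above, which gives every dosed patient a valid outcome.

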2. TRIAL RATIONALE

2.1. Relevance of the trial

Acute cerebral circulatory disorders (ACCD) are a problem of great medical and social importance due to the significant frequency of their development, high rate of disability and mortality [Evzelman M. A. and Alexandrova N. A., 2013]. Stroke includes ACCD, characterized by the sudden (within minutes, less often - hours) appearance of focal neurological symptoms (motor, speech, sensory, coordinator, visual and other disorders) and/or general cerebral disorders (changes in consciousness, headache, vomiting, etc.), which persist for more than 24 hours or lead to the death of the patient in a shorter period of time due to the cause of cerebrovascular origin [Vereshchagin N. V. et al., 2002].

The annual stroke mortality rate in Russia is one of the highest in the world (175 cases per 100,000 population per year). According to the National Stroke Association register, 31 per cent of stroke patients require assistance to care for themselves and 20 per cent are unable to walk independently. Residual phenomena after stroke are detected in about 2/3 of patients, of which 50% - cognitive impairment, which limits social adaptation, including labour activity and self-care in the home, even in the absence of significant motor impairment [Evzelman M. A. and Alexandrova N. A., 2013; Stakhovskaya et al., 2012].

The most common in clinical practice is ischaemic stroke (IS) - ACCD, accompanied by

damage to brain tissue, impairment of its functions due to obstruction or cessation of blood flow to one or another part [Evzelman M. A. and Alexandrova N. A., 2013]. According to the register of brain stroke, conducted by the Research Institute of Neurology RAMS (Scientific Centre of Neurology), by the end of the acute period (3 weeks from the onset of the disease) hemiparesis is observed in 81.2% of surviving patients, including hemiplegia - 11.2%, arthropathy - 15-20%, aphasia - 35.9%, dysarthria - 13% [Fedin A. I. et al., 2009].

The pathomorphological basis of ischaemic strokes is a variety of pathogenetic factors leading to the formation of ischaemic foci in cerebral structures. The pathogenesis of cerebral structures lesions in acute stroke is usually homogeneous, despite the background variety of causes that cause them, and it consists in disorders of energy synthesis [Fedin A. I. et al., 2009]. The accumulated experience has shown that the zone of irreversible changes in the brain during an IS increases gradually, with the development of one or another stage of the ischaemic cascade [Gusev E. Gusev. I. and Skvortsova V. I., 2002].

The main directions of therapy of ischaemic stroke in the acute period are reperfusion (thrombolytic therapy, anticoagulants) and primary neuroprotection aimed at interruption of fast glutamate-calcium channel mechanisms in order to correct the imbalance of excitatory and inhibitory neurotransmitter systems. It is recommended to start this type of neuroprotection from the first minutes of ischaemic stroke and to continue it during the first 3 days, especially actively during the first 12 h of the disease. Secondary neuroprotection is aimed at interrupting the delayed mechanisms of cell death (on the distant consequences of ischaemia) and includes the use of inhibitors of pro-inflammatory cytokines and adhesion molecules, antioxidants, trophic factors, neuropeptides [Novikova L. B. et al., 2013].

Stimulation of the metabolic chain of the Krebs cycle is considered a promising way to improve the energy supply of the cell. This effect can be achieved by using succinate-containing substances, in particular, Mexidol® (2-ethyl-6-methyl-3-hydroxypyridine succinate). Mexidol® exhibits antioxidant and antiradical properties, has a wide range of effects on various mechanisms of regulation and metabolic activity of cells [Fedin A. I. et al., 2009].

In the course of experimental studies, the effect of Mexidol® on the development of excitotoxicity *in vitro* was shown. Mexidol® inhibits the development of glutamate-induced neurotoxicity, ascorbate-dependent (non-enzymatic) and NADPH2-dependent (enzymatic) iron-induced lipid peroxidation, has the ability to bind superoxide anion radical, increases the activity of Se-dependent glutathione peroxidase. These effects underlie its antioxidant and antihypoxant action [Shchulkin A. V., 2013]. The results of chemoreactomic analysis of ethylmethylhydroxypyridine succinate molecule showed that the main targets of its pharmacological action are acetylcholine and GABA-A receptors, COX-2 enzymes, 5-LOG and PPAR-receptor [Torshin I. Yu et al., 2016].

During the trial of efficacy and safety of Mexidol®, its effect on the dynamics of neurological manifestations of the disease, emotional status and quality of life in patients with chronic cerebral ischaemia it was found that by the end of the trial in the patients of the main group significantly decreased the severity of motor activity disorders, normalized quality of life indicators (SF-36 scale), there was a significant improvement in the indicators of cognitive functions. High efficacy and safety of treatment of patients with chronic cerebral ischaemia with Mexidol® has been confirmed [Chukanova E. I. et al., 2015].

Thrombolytic therapy (TLT) in combination with the use of Mexidol® leads to a significantly faster reduction in the severity of neurological deficit and somatic complications. TLT in combination with Mexidol® creates conditions not only for the recovery of neurological functions, but also for the prevention of reactions of secondary brain damage [Chefranova Zh. Yu et al., 2012]. It was found that the inclusion of Mexidol® in the scheme of complex rehabilitation treatment significantly improves the results of rehabilitation of patients, contributing to both an increase in the degree of recovery of neurological functions and an increase in the level of everyday adaptation [Kovalchuk V. V., 2011]. The positive effects of

Mexidol® in patients in the acute period of AI were demonstrated: there was a complete regression of general cerebral symptoms and marked regression of focal deficit, which determined the feasibility of using Mexidol® in complex therapy [Shevchenko L. A. et al., 2006].

In elderly patients in the recovery period of ischaemic stroke, therapy with Mexidol® improved well-being, memory and mnemonic functions, reduced the level of depression. The patients had a wider range of social and domestic activity, reduced spasticity, improved cerebral blood circulation and activated the relationship between hemodynamics in the extra- and intracranial vessels of the carotid basin, indicating the activation of metabolic processes in the brain [Kuznetsova S. M. et al., 2009].

The efficacy and safety of long-term sequential therapy with Mexidol® compared to placebo was evaluated in the EPICA clinical trial in patients in the acute and early recovery periods of hemispheric AI. Treatment with Mexidol® showed a significant reduction in symptoms and functional impairment, there was significantly more pronounced compared to placebo improvement in life activity, measured on a modified Rankin scale: 0-2 points on the modified Rankin scale, was observed in 96.7% of patients in the group of Mexidol® and 84.1% in the placebo group($p=0.039$) [Stakhovskaya L. V. et al., 2017].

At the end of therapy, the neurological deficit was significantly lower in the Mexidol® therapy group when tested by the stroke scale of the National Institutes of Health vs. placebo. Mexidol® therapy contributed to a significant improvement in the quality of life starting from the 2nd visit. The vast majority of patients in the group of therapy with Mexidol noted that they had no problems with movement, self-care, performance of daily activities, did not experience pain and discomfort, anxiety and depression. In the subpopulation of patients with diabetes mellitus in the group of therapy with Mexidol® the quality of life was significantly higher by the end of therapy [Stakhovskaya L. V. et al., 2017].

Thus, the efficacy and safety of Mexidol® therapy in patients with MI in the acute and early recovery periods have been proved in a number of studies.

